#### Vaccination status ascertainment

The exposure of interest in this study will be vaccination history with trivalent influenza vaccine (for seasonal vaccine) and vaccination history with the pandemic vaccine (once the vaccine becomes available). The vaccination history includes date of administration and brand names. Documenting the flu batch codes will allow identifying the vaccine brand, the vaccine content (seasonal, pandemic) and the dose.

An individual is considered as vaccinated against influenza if:

- he or she reports having received an influenza vaccination during the current season; or
- he or she is registered as vaccinated in a vaccination registry;
- or
- his or her insurance company can show evidence of pharmacy delivery or re-imbursement of influenza vaccine/vaccination during the current influenza season.
- Pandemic vaccine: The number of doses will be documented.
  - **b** Seasonal and pandemic vaccines used will be detailed in the study annexes.
  - **b** The precise mode of vaccine ascertainment for each study will be specified in the study annexes.

## 3.9 Risk groups

#### Seasonal vaccine

Individuals will be considered to belong to a risk group if this is indicated in the GP records or if the patient reports suffering from one of the underlying conditions included in the interview questionnaire (see below).

#### Pandemic vaccine

According to ECDC

(http://www.ecdc.europa.eu/en/publications/Publications/Forms/ECDC\_DispForm.aspx?ID=388; 25 August 2009), the risk groups to be considered for the pandemic vaccine are:

- people aged less than 65 years with chronic underlying conditions, namely:
  - chronic respiratory diseases;
  - chronic cardiovascular diseases;
  - chronic metabolic disorders (notably diabetes);
  - chronic renal and hepatic diseases;
  - persons with deficient immunity (congenital or acquired);
  - chronic neurological or neuromuscular conditions;
  - any other condition that impairs a person's immunity or prejudices their respiratory function;
  - young children (especially under the age of 2 years); and
- pregnant women.

The target groups may differ between countries. Other risk groups may be added during the pandemic.

**b** Risk groups for each study will be listed in the study annexes.

# 3.10 Confounding factors and effect modifiers

#### **Chronic diseases**

Seasonal vaccine:

The list of underlying conditions in the questionnaire should include at least those for which the vaccine is recommended in the study country and may include:

- diabetes, if treated for insulin-dependent or non-insulin-dependent diabetes;
- cardiovascular disease: myocardial infarction, angioplasty, coronary artery bypass surgery, stroke, transient ischemic attacks, treated hypercholesterolemia, treated hypertension;
- chronic pulmonary disease (asthma, chronic bronchitis, bronchopulmonary dysplasia, cystic fibrosis);
- chronic renal diseases (chronic renal failure);
- immunodeficiency (conditions that suppress the immune function due to underlying disease and/or therapy – e.g. people receiving chemotherapy, HIV infection); and
- anaemia.

**b** The list of chronic diseases for which the seasonal vaccine is recommended will be part of the study annexes.

Pandemic vaccine:

The list of underlying conditions in the questionnaire should include all conditions that define the risk groups in each of the study countries (see 'risk groups' above).

**b** The list of chronic diseases for which the pandemic vaccine is recommended will be part of the study annexes.

## **Severity**

The severity of the underlying conditions will be measured by the number of hospital admissions due to underlying conditions in the 12 months prior to inclusion in the study.

## **Smoking history**

Smoking history will be collected and coded as follows: never-smoker, former smoker (stopped smoking at least one year before inclusion in the study), current smoker.

## **Previous vaccinations**

Vaccination against seasonal influenza in the last two seasons (recording vaccination information for each influenza season).

#### **Functional status**

Low functional status will be defined as needing help to bathe or to walk.

## Number of GP consultations in the previous 12 months

In order to document and control for access to care in the various control groups, the number of all GP visits in the 12 months before inclusion in the study will be recorded.

## **Antiviral administration**

Use of antivirals will be documented: type and date of administration.

## Source of information

Data will be collected using a standardised questionnaire. For cases and controls selected at GP practices, data will be collected face-to-face.

Seasonal vaccine: For community controls, the procedures for data collection will be defined by each study coordinator.

**b** The precise modes of data collection for community controls will be specified in the study annexes.

If GPs use electronic medical records, information on collected variables can be extracted from these records to validate the information collected through the standardised questionnaire.

## 3.11 Sample size

A minimum of 30 GPs will be required for each of the studies.

Providing VE estimates for each separate study is one of the objectives of this project. Therefore, the minimum sample size should be estimated for each study in order to obtain precise VE estimates. The pooled analyses should not prevent study teams to include a big enough sample size to obtain exact estimates for each separate study.

**b** The sample size calculation for each study will be detailed in the study annexes.

Table 1 illustrates the various sample sizes that would ensure an alpha error of 0.05, a power of 0.8 or 0.9, a detectable odds ratio ranging from 0.3 to 0.6, and a vaccine coverage among the source population (or among controls) ranging from 50 to 70 %.

Power	Alpha	Controls/	Vaccine coverage in source	Detectable	Number of	Number of
		case	population/controls	OR	cases	controls
0.90	0.05	1	0.5	0.6	345	345
0.80	0.05	1	0.5	0.6	262	262
0.90	0.05	1	0.5	0.5	194	194
0.80	0.05	1	0.5	0.5	148	148
0.90	0.05	1	0.5	0.4	116	116
0.80	0.05	1	0.5	0.4	89	89
0.90	0.05	1	0.5	0.3	72	72
0.80	0.05	1	0.5	0.3	56	56
0.90	0.05	1	0.6	0.6	341	341
0.80	0.05	1	0.6	0.6	259	259
0.90	0.05	1	0.6	0.5	188	188
0.80	0.05	1	0.6	0.5	144	144
0.90	0.05	1	0.6	0.4	110	110
0.80	0.05	1	0.6	0.4	85	85
0.90	0.05	1	0.6	0.3	67	67
0.80	0.05	1	0.6	0.3	52	52
0.90	0.05	1	0.7	0.6	370	370
0.80	0.05	1	0.7	0.6	281	281
0.90	0.05	1	0.7	0.5	200	200
0.80	0.05	1	0.7	0.5	153	153
0.90	0.05	1	0.7	0.4	115	115
0.80	0.05	1	0.7	0.4	88	88
0.90	0.05	1	0.7	0.3	67	67
0.80	0.05	1	0.7	0.3	52	52

Table 1: Sample size calculations

The sample size should be respected for each population subgroup for which a sub (stratified) analysis (e.g. effect modification) is planned.

## 3.12 Data

Data on cases and GP controls will be collected at GP office level. GPs interview the patients using a standardised questionnaire. GPs using electronic medical records can extract some or all of the variables from these records (e.g. vaccination status, chronic diseases based on ICD codes).

**b** Data collection methods for the community controls will be detailed in the study annexes.

EpiConcept may develop an electronic questionnaire and a web-based questionnaire for participating GPs.

Double data entry will be required unless medical electronic records are used.

**b** Details on data collection methods, data entry and data transmission will be available in the study annexes.

#### **Collected information**

Collected information will include (see also Annex 1: List of variables, definition and coding):

- study identification: country and GP;
- case/control demographics;
- signs, symptoms;
- date of onset of ILI;
- date of swabbing;

- laboratory results;
- selected underlying chronic conditions (including diabetes, heart disease, chronic obstructing pulmonary disorder, renal diseases, and immunodeficiencies);
- number of hospitalisations for chronic diseases in the previous 12 months;
- total number of GP visits in the previous 12 months;
- smoking history;
- current season influenza vaccination including date;
- pandemic vaccination including number of doses, date, brand;
- influenza vaccination in the previous two seasons;
- pregnancy status;
- functional status;
- antiviral administration; and
- information on laboratory confirmed A(H1N1)v influenza since the beginning of the pandemic.

Pandemic vaccine: Collected data will be revised as more information on the vaccine and the target groups becomes available.

## **Data validation**

A sample of paper questionnaires will be checked against the study database to validate data entry.

For GPs using electronic medical records, a sample of questionnaires will be checked against the medical records and against the study database.

The agreement between patient vaccine records/vaccination status reported by study participant/vaccine registries will be measured.

**b** The specific validation procedures, including sample size calculation for questionnaire validation (if applicable), will be specified in the study annexes.

## 3.13 Analysis

Seasonal vaccine: Analysis will be restricted to the groups in each of the participating countries for which seasonal vaccine is recommended.

Pandemic vaccine: Analysis will be restricted to the groups in each of the participating countries for which the pandemic vaccine is recommended.

Analysis will be carried out first for each individual study. In a second step, a pooled analysis is conducted.

All analyses will be done separately for seasonal and pandemic vaccine.

Analyses will be conducted for:

- all data restricted to cases/controls from which swabs were taken < 4 days since the date of onset of symptoms;
- overall VE and strain-specific VE, sample size permitting; and
- the pooled analysis, separately for studies with different control groups (using an unmatched or a matched analysis as appropriate).

Pandemic vaccine: In addition, analysis is conducted for each specific brand.

#### Individual study analysis

#### Descriptive and univariable analysis

The proportion of eligible ILI cases and controls who accepted to participate in the study will be calculated (response rate).

Study participants will be described by baseline characteristics. Baseline characteristics of cases and controls in unmatched studies will be compared using the chi-square test, Fisher's exact test, t-test or the Mann-Whitney test (depending on the nature of the variable and the sample size). In matched case-control studies, characteristics of cases and controls will be compared using McNemar's chi-square test, paired t-test, conditional logistic regression, or the Wilcoxon signed-rank test (depending on the nature of the variable and the number of controls).

The association between vaccination status and baseline characteristics will be measured for both case and control groups.

#### Measure of effect

Vaccine effectiveness will be computed as VE = 1 - OR. An exact 95 % confidence interval will be computed around the point estimate. (For studies using the screening method, refer to the ECDC generic screening protocol.)

#### Stratified analysis

Analysis will be stratified according to:

Seasonal vaccine:

- Age groups < 75 years and > 74 years.
- Presence or absence of high-risk conditions.
- Time: early influenza season, peak, late influenza season.
- Virus strain.

Pandemic vaccine:

- Vaccine brand.
- Time: different periods defined by pandemic vaccine availability.
- Target groups.

A sufficient sample size should be planned in order to ensure enough individuals in each stratum for a precise estimate. For example, assuming a vaccination coverage of 50% and a VE of 60%, studies should aim to have at least 90 cases and 90 controls in each of the strata. Effect modification will be assessed comparing the OR across the strata of the baseline characteristics. Confounding will be assessed by comparing crude and adjusted OR for each baseline characteristic.

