# **3.7 Controls**

Various control groups can be selected depending on the available resources. All studies will include at least control group 1 (ILI influenza negative) as defined below.

- Seasonal vaccine: countries will assess whether other control groups could be used in addition to control group 1 (control group selection depends on feasibility).
- **b** The various control groups selected by each study will be detailed in the study annexes.
- Control group 1, ILI flu negative:
  - ILI cases that tested negative for influenza will be included in control group 1.
- Control group 2, non-ILI GP clients (density case-control design):
  - Controls will be selected among GP clients seen at the GP office and selected concurrently to cases (+/- one week from the date of consultation of the corresponding case). Controls will be selected by simple or systematic random sampling among clients who did not yet develop ILI during the influenza season.

**b** Procedures for selection in each of the studies will be detailed in the study annexes. If feasible, controls should be matched by age group (< 75 years; >= 75 years).

- Control group 3, GP clients (case-cohort design):
  - Controls will be selected randomly from a list of GP patients.
  - **b** Procedures for selection in each of the studies will be detailed in the study annexes.
- Control group 4, community controls (density case-control design):
  - Controls are randomly selected individuals living in the same geographical area (defined by postcode or other geographical/administrative division) as the corresponding case. Control individuals have not suffered from ILI during the current influenza season until the corresponding case became ill.
    - **P** Procedures for selection will be detailed in the study annexes.
    - If feasible, controls should be matched by age group (< 75 years; >= 75 years).
- Control group 5, community controls (case cohort):
  - Controls will be randomly selected individuals living in the same geographical area of the corresponding case.
    - **P** Procedures for selection will be detailed in the study annexes.
    - If feasible, controls may be matched by age group (< 75 years; >= 75 years).
- Control group 6, community controls (screening method):
  - For each of the target age groups, vaccine coverage of cases will be compared with the vaccine coverage of the population in the GP catchment area.

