#### Multivariable analysis

A multivariable (conditional if matched) logistic regression analysis will be conducted to control for negative and positive confounding. Odds ratios and standard errors will be obtained. Variables will be tested for multicollinearity. Interactions will be tested using the likelihood ratio test or Wald's test and will be included in the model if significant at the 5 % level. Factors other than statistical significance will also be used as criteria for inclusion of an interaction term.

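### In studies with 1:1 matched controls and a conditional analysis, splitting by high-risk condition discards risk-discordant pairs, and the target of 90 cases and 90 controls per stratum does not guard against it

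*Protocol*

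**What the plan says.** Section 2.2 makes VE by risk group a secondary objective. For the seasonal vaccine, section 3.13 (Stratified analysis) includes among its strata "Presence or absence of high-risk conditions" and judges effect modification by comparing odds ratios between strata. Annex 3 (Stratified analysis) repeats the two-stage pooled analysis in each stratum, again naming high-risk conditions.

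On the model, section 3.13 states: "A multivariable (conditional if matched) logistic regression analysis will be conducted to control for negative and positive confounding". Interaction terms are kept mainly when significant at 5%, although other considerations may also count.

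On controls, section 3.7 states: "All studies will include at least control group 1 (ILI influenza negative) as defined below". No matching is described for that group. Groups 2, 4 and 5 are optional. Their descriptions refer to a corresponding case, and matching on two age bands is asked for where feasible (groups 2 and 4) or permitted (group 5). Group 2 controls are also "selected concurrently to cases (+/- one week from the date of consultation of the corresponding case"), and groups 4 and 5 come from the case's area. Risk status is never a matching factor. Annex 1 carries a variable linking controls to their case.

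On size, section 3.13 says that "studies should aim to have at least 90 cases and 90 controls in each of the strata", for 50% coverage and VE of 60%. Section 3.11 gives the basis as "an alpha error of 0.05, a power of 0.8 or 0.9", and every row of Table 1 has one control per case.

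**The concern.** A conditional likelihood learns only from sets that contain a case and at least one control. If the file is cut on a variable that was not matched, a 1:1 pair whose members fall on different sides of the cut contributes to neither stratum. Age bands, where they are matched, keep pairs whole. High-risk condition does not.

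The per-stratum target does not catch this because it counts individuals. A matched study can count 90 cases and 90 controls among its high-risk participants, conclude that it is adequately sized, and then fit a conditional model to far fewer pairs. What is at stake is precision for a named secondary objective, lost although the data have been collected. Validity is not in question.

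**Working it through.** **1. The plan's own figure.** Coverage in controls is 0.5 and the odds ratio is 0.4. Vaccinated proportion in cases = 0.4 × 0.5 / (1 + 0.5 × (0.4 − 1)) = 0.2/0.7 = 0.286. The formula for two independent proportions (two-sided alpha 0.05, power 0.80) gives 81 per group, or 90 with the continuity correction. Tables 1 and 2 state 89 and the text uses 90. All 24 rows of Table 1 reproduce to within one subject with the correction, and none without it. The target is therefore an unmatched number.

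**2. Pairs needed.** Take vaccination as independent within pairs (an assumption).

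- Case vaccinated, control not: 0.286 × 0.5 = 0.143.
- Control vaccinated, case not: 0.714 × 0.5 = 0.357.
- Discordant total s = 0.5; difference d = 0.214.
- McNemar pairs for 80% power: (1.96√s + 0.842√(s − d²))² / d² = 83.1.
- Power with n pairs: Φ[(d√n − 1.96√s) / √(s − d²)], which is 83% at n = 90.

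So the target works for a matched analysis only if about 83 of 90 pairs (92%) stay intact.

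**3. Pairs kept.** Let q be the share of controls with a high-risk condition. The documents give no value, so a range is shown. With 1:1 pairs and risk independent within pairs, 90 high-risk cases keep 90q pairs and 90 low-risk cases keep 90(1 − q).

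| q | High-risk pairs kept | Power | Low-risk pairs kept | Power |
|---|---|---|---|---|
| 0.2 | 18 | 24% | 72 | 74% |
| 0.3 | 27 | 34% | 63 | 68% |
| 0.5 | 45 | 53% | 45 | 53% |
| 0.7 | 63 | 68% | 27 | 34% |
| 0.8 | 72 | 74% | 18 | 24% |

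Each entry is per 90 cases in that stratum. The rarer stratum bears the loss in practice. If 20% of cases are also high risk, reaching 90 high-risk cases takes 90/0.2 = 450 cases. The 360 low-risk cases then keep 360 × 0.8 = 288 pairs, which is ample.

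**4. What softens it.** A within-pair correlation in risk of 0.2 at q = 0.5 raises the pairs kept to 90 × (0.5 + 0.2 × 0.5) = 54. With m controls per case, a high-risk case keeps at least one same-stratum control with probability 1 − (1 − q)^m. At q = 0.5 that is 75%, 88% and 94% for m = 2, 3 and 4.

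**5. Is the loss avoidable?** Simulations of 180 pairs at q = 0.5 compared the split conditional analysis with one conditional model on all pairs that has risk and vaccine-by-risk terms. Results are for the high-risk stratum.

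| Risk OR (assumed) | Pairs left after split | Split: SE of log OR, power | One model: SE of log OR, power |
|---|---|---|---|
| 1 | 45 | 0.47, 52% | 0.33, 82% |
| 1.5 | 54 | 0.43, 61% | 0.32, 86% |

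Hand check of the split: SE = √(1/(0.143n) + 1/(0.357n)), which is 0.47 at n = 45 and 0.43 at n = 54. In the second row about 108 cases and 90 controls are high risk, so the per-stratum target is met on paper.

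**The case against.** The strongest reply is that the protocol never says to split matched sets and run a conditional model in each half. Section 3.13 provides for interaction terms and lets reasons other than significance bring them in. It also leaves the pooled analysis matched or unmatched, as suits the design. Annex 3 (Controlling for GP effect) names simple logistic regression for the individual study estimates. The example syntax in Annex 6 is unconditional, with age band and calendar week as covariates. Such a model, run within risk strata, discards nobody. Control group 1 is in every study and is unmatched. The 90/90 figure is itself offered as an example, and sample sizes are left to the study annexes.

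Most of this stands, and it confines the point to optional control groups, individual matching at or near 1:1, and a conditional analysis. It does not remove the point. Stratification is the route that section 3.13 and Annex 3 actually name for VE by risk group. Annex 3 repeats the same two-stage analysis in each stratum, and section 3.13 makes the regression conditional for matched data. A matched study that follows those sentences in order arrives at the lossy analysis. The interaction route is tied mainly to significance, whereas VE by risk group has to be reported either way.

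A reader might infer that half the information is lost as a rule, or that VE by risk group is underpowered throughout the project. The documents support neither. Half needs 50% prevalence, one control per case and no within-pair correlation in risk, and the mandatory control group does not have the problem.

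**Conclusion.** The point holds as a minor, conditional one. With an individually matched control group 2, 4 or 5 and a conditional analysis, stratifying by high-risk condition drops all 1:1 pairs discordant on risk, and meeting 90/90 does not ensure the roughly 83 pairs that 80% power requires. Over assumed prevalences of 20% to 80%, 90 cases in a stratum keep between 18 and 72 pairs, so power runs from 24% to 74%. With about half of participants high risk, one model on all pairs restores power from 52–61% to 82–86%. These figures assume OR 0.4, 50% coverage, one control per case, and independence of vaccination and of risk within pairs. Several controls per case, or positive correlation of risk within pairs, makes the loss smaller. Nothing here affects control group 1 or an unmatched adjusted analysis.

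**What to change.** In section 3.13 and in Annex 3 (Stratified analysis), add that for matched control groups VE by risk group is estimated from one conditional logistic model on all matched sets. The model should contain the risk condition and vaccine-by-risk-group terms, kept whether or not the interaction is significant. The resulting risk-group log odds ratios and standard errors then enter the two-stage pooling. Where matching is only on age band and time, an unmatched model adjusted for those factors is an acceptable alternative.

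The cost is a sentence or two and one model in place of two, with no extra data. The downside is that the other covariates are assumed to act equally in both risk groups unless their product terms are added.

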#### Multivariable analysis

A multivariable (conditional if matched) logistic regression analysis will be conducted to control for negative and positive confounding. Odds ratios and standard errors will be obtained. Variables will be tested for multicollinearity. Interactions will be tested using the likelihood ratio test or Wald's test and will be included in the model if significant at the 5 % level. Factors other than statistical significance will also be used as criteria for inclusion of an interaction term.

